7.1 Subgroup analyses

Exploratory analyses will be reported using 99% confidence intervals. Logistic regression will be used with interaction terms (treatment group by subgroup) for the following subgroups:

- (i) Presence of ARDS prior to randomisation
- (ii) Baseline PaO₂ /FiO₂ ratio prior to randomisation (<50/50-99/100-150)
- (iii) Baseline Plateau Pressure prior to randomisation quartiles
- (iv) Volume of ECCO₂R participants at center (<10/>=10)
- (v) Vasopressor requirement prior to randomisation (yes/no)
- (vi) Baseline PaCO₂ prior to randomisation quartiles
- (vii) Baseline driving pressure prior to randomisation quartiles
- (viii) Baseline risk of death score (Apache II) quintiles prior to randomisation.

[figure not shown]

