1.3 Inclusion criteria

- Invasive mechanical ventilation using PEEP ≥ 5cmH₂O*
- Acute and potentially reversible cause of acute respiratory failure as determined by the treating physician
- Within 48 hours of the onset of hypoxaemia as defined by PaO₂/FiO₂ ≤ 20kPa**

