1.4 Exclusion criteria

- Age < 16 years old
- Intubated and mechanically ventilated via an endotracheal or tracheostomy tube ≥ 7
 days (168 hours) up to the time of randomisation
- Ability to maintain Vt to ≤ 3ml/kg PBW while maintaining pH ≥ 7.2 as determined by the treating physician*
- Receiving, or decision to commence, ECMO in the next 24 hours.
- Mechanical ventilation using High Frequency Oscillatory Ventilation (HFOV) or Airway Pressure Release Ventilation (APRV)
- Untreated pulmonary embolism, pleural effusion or pneumothorax as the primary cause of acute respiratory failure.

Doc No: ST06-RD01 Page **6** of **35**

^{*}Recommended on low tidal volume ventilation ≤ 6ml/kg PBW

^{**}Requires two ABG with a PaO2/FiO2 \leq 20kPa separated by at least 6 hours. 48 hour duration to consent begins at the time of 2nd ABG demonstrating PaO2/FiO2 ratio \leq 20kPa. Site will then have a further 8 – 24 hours to randomise and administer the intervention. The onset of hypoxaemia is from time of intubation and invasive ventilation.(ABGs with PaO2/FiO2 \geq 20kPa are permitted between the two trial inclusion ABGs).

- Acute respiratory failure fully explained by left ventricular failure or fluid overload (May be determined by clinical assessment or echocardiography/cardiac output monitoring).
- Left ventricular failure requiring mechanical support
- Contra-indication to limited systemic anticoagulation with heparin
- Unable to obtain vascular access to a central vein (internal jugular or femoral vein)
- Inferior vena cava filter (if using femoral vein catheter)
- Consent declined
- Treatment withdrawal imminent within 24 hours
- Patients not expected to survive 90 days on basis of premorbid health status
- Do Not Attempt Resuscitation (DNAR) order (excluding advance directives) in place
- Severe chronic respiratory disease requiring domiciliary ventilation (except for sleep disordered breathing)
- Severe chronic liver disease (Child Pugh >11)
- Platelet count < 40,000 mm³ (Prior to catheter insertion)
- Previously enrolled in the REST trial
- Prisoners

[figure not shown]
Full details of the background to the trial and its design are presented in the protocol.

Doc No: ST06-RD01 Page **7** of **35**

^{*} This exclusion criterion relates to whether a Vt \leq 3ml/kg PBW could be achieved without the need for ECCO₂R. A tidal volume \leq 3ml/kg is unlikely to be achievable in most clinical scenarios without ECCO₂R as it is approaching dead space ventilation.

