3.3 Data completion schedule

Study Visits and Procedures

Clinical data will be collected during trial participants stay in the ICU up to 28 days after randomisation. For routinely collected clinical data the NHS record will be the source document and for study specific clinical measurements the CRF will be the source document.

Day 0 (baseline)

Day 0 is 24 hours prior to randomisation. If more than one value is available for this 24-hour period, the value closest but prior to the time of randomisation will be recorded. Day 0 (baseline) data collected will include but is not limited to:

- Patient demographics (date of birth, gender, measured height)
- ICNARC Case Mix Programme (CMP) number
- Scottish Intensive Care Society Audit Group (SICSAG) number
- Date/time of consent and randomisation
- Date and time of ICU admission
- Admission diagnostic category
- Assessment of functional status
- Presence of Acute Respiratory Distress Syndrome (ARDS) and aetiology
- Date/time of onset of mechanical ventilation
- The Acute Physiology and Chronic Health Evaluation score (APACHE II)

Doc No: ST06-RD01 Page **10** of **35**

- PaO₂/FiO₂ ratio (Qualifying PaO₂ /FiO₂ ratios including date/time)
- Date and time of worst PaO₂/FiO₂ ratio
- Determinants of Sequential Organ Failure Assessment (SOFA) score
- Ventilation parameters including but not limited to: Mode of ventilation, minute volume, RR, mean airway pressure, plateau pressure, PEEP
- Arterial blood gas including but not limited to FiO₂, PaO₂, PaCO₂, pH
- Date/time onset of ECCO₂R therapy (from commencement of CO₂ removal)
- Use of adjunctive therapies including Neuromuscular Blocking Drugs (NMBD) and prone position
- Echocardiography parameters including but not limited to ventricular size and function and tricuspid annular plane systolic excursion (TAPSE)

Daily Data:

Day 1 is from the time of randomisation to the end of that calendar day. If more than one value is available for this period, the value closest but after the time of randomisation will be recorded. All other daily measurements will be recorded and collected between 6-10am or as close to this time as possible, unless otherwise stated in the CRF. Daily data will be collected to day 7 and will include but is not limited to:

- Ventilation parameters including but not limited to: Mode of ventilation, minute volume, RR, mean airway pressure, plateau pressure, PEEP
- Arterial blood gas including but not limited to FiO₂, PaO₂, PaCO₂, pH

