8.3 Baseline Characteristics

- Age, mean (SD) by treatment arm
- Gender, no. (%) by treatment arm
- Dependency prior to hospital admission, no. (%) by treatment arm
- Height (cm), mean (SD) by treatment arm
- Predicted body weight (kg), mean (SD) by treatment arm
- Admission diagnostic category, no. (%) by treatment arm
- Presence of ARDS, no. (%)by treatment arm
- Aetiology of Ards, no. (%) by treatment arm
- APACHE II score, mean (SD) by treatment arm
- Arterial blood gas PaCO₂, mean (SD) by treatment arm
- PaO₂/FiO₂ ratio closest to but prior to randomisation, mean (SD) by treatment arm
- Second qualifying PaO₂/FiO₂ ratio, mean (SD) by treatment arm
- Worst PaO₂/FiO₂ ratio, mean (SD) by treatment arm
- Arterial pH, mean (SD) by treatment arm
- Total SOFA score, mean (SD) by treatment arm
- Mode of ventilation, no. (%) by treatment arm
- Use of Adjunctive therapies, no. (%) by treatment arm
- Mean airway pressure (cmH₂O), mean (SD) by treatment arm
- PEEP (cmH₂O), mean (SD) by treatment arm
- Plateau Pressure (cmH₂O), mean (SD) by treatment arm
- Total Respiratory Rate (breaths/min), mean (SD) by treatment arm
- Minute Volume (L/min), mean (SD) by treatment arm
- Tidal Volume (ml/kg PBW), mean (SD) by treatment arm

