Appendix 1: P/F ratio reference table for inclusion criteria

FiO ₂	Maximum PaO2 if P/F ratio ≤ 20kPa
0.50	10.0 kPa
0.55	11.0 kPa
0.60	12.0 kPa
0.65	13.0 kPa
0.70	14.0 kPa
0.75	15.0 kPa
0.80	16.0 kPa
0.85	17.0 kPa
0.90	18.0 kPa
0.95	19.0 kPa
1.00	20.0 kPa

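### The exploratory PaO₂/FiO₂ subgroup uses bands with no unit that stop at the entry limit, so a patient whose ratio has risen above 150 mmHg by baseline has no band

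*SAP*

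**What the plan says.** - **Bands.** SAP 7.1, item (ii), lists the baseline PaO₂/FiO₂ "ratio prior to randomisation (<50/50-99/100-150". The subgroup figure in Appendix 3 has the same three rows. Neither place gives a unit, and neither has a row above 150.
- **Unit.** The inclusion criterion in 1.3 sets the limit at 20 kPa. Appendix 1 is headed "Maximum PaO2 if P/F ratio ≤ 20kPa". The sample-size sources in section 5 are also in kPa. The baseline lists in 8.3 and Appendix 3 give no unit for this ratio.
- **Which value is baseline.** For Day 0, the 24 hours before randomisation, section 3.3 says that where several values exist "the value closest but prior to the time of randomisation will be recorded". Section 8.3 has one row for the "ratio closest to but prior to randomisation, mean (SD) by treatment arm" and separate rows for the second qualifying ratio and the worst ratio.
- **Timing.** The double-asterisk footnote to the inclusion criteria (printed with 1.4) starts a 48-hour period to consent at the second qualifying gas. It then adds "Site will then have a further 8 – 24 hours to randomise and administer the intervention".
- **Status.** Section 7.1 describes the subgroup analyses as exploratory, with 99% confidence intervals and a treatment-by-subgroup term in logistic regression.

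**The concern.** A subgroup factor should place every randomised patient in exactly one level. Here the upper edge comes from the entry criterion, while the variable being banded is a later measurement that need not satisfy that criterion. Patients who improved between qualifying and randomisation have no level, and the SAP has no rule for them. A logistic model fitted to the coded factor would drop them, and they are the mildest cases at baseline. The comparison across severity would then lack its mild end.

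The missing unit adds a coding decision. Section 6.2 says that data analysts are not blinded to allocation. The unit, the choice of ratio and the handling of values above 150 could therefore all be settled by people who know the allocation, which weakens the pre-specification.

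**Working it through.** **1. The plan's own figure.** Appendix 1 should equal 20 × FiO₂: 20 × 0.50 = 10.0 kPa, and so on up to 20 × 1.00 = 20.0 kPa. All 11 rows reproduce exactly, so the trial's working unit is kPa and its ceiling is 20.

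**2. Unit of the bands.** With 1 kPa = 7.50062 mmHg:
- 20 kPa × 7.50062 = 150.01 mmHg, which is the upper edge of the top band.
- 50, 100 and 150 mmHg are 6.67, 13.33 and 20.00 kPa.
- Read as kPa, the first cut-point would be 50 × 7.50062 = 375 mmHg, far above the entry limit.

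mmHg is therefore the only sensible reading. Two small edge effects follow from converting without a rounding rule. A ratio of exactly 20.0 kPa becomes 150.01 and misses the top band, and a converted value between 99 and 100 falls between two bands.

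**3. Can baseline exceed 150 mmHg?** Consent may come up to 48 hours after the second qualifying gas, whereas the Day 0 window is 24 hours. The qualifying gas can therefore be older than the baseline window. No passage requires the ratio still to be at or below 20 kPa at randomisation. So baseline values above 150 mmHg are possible, and they have no band.

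**4. Illustrative size.** The only mean in the SAP is 15 kPa (section 5), from the ventilation trial cited for the sample size, not from this population. The SD is an assumption, 3 to 6 kPa. For a normal distribution the shares are Φ((6.67 − 15)/SD) and 1 − Φ((20 − 15)/SD). A lognormal with the same mean and SD is shown for comparison. Counts are of 1120.

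| Assumed SD (kPa) | Below 50 mmHg, normal | Above 150 mmHg, normal | Below 50, lognormal | Above 150, lognormal |
|---|---|---|---|---|
| 3 | 0.3% (3) | 4.8% (54) | 0.0% | 6.0% |
| 4 | 1.9% (21) | 10.6% (118) | 0.2% | 11.0% |
| 5 | 4.8% (54) | 15.9% (178) | 1.0% | 14.7% |
| 6 | 8.2% (92) | 20.2% (227) | 2.8% | 17.4% |

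If only values at or below 20 kPa are counted, the lowest band holds 0.3% to 10.3% (normal) or 0.0% to 3.4% (lognormal).

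**5. What a sparse band can show.** Take 54 patients, 27 per arm, with mortality of 41% and 32% (section 5: 41% less 9 points). The variance of the log odds ratio is 1/(27 × 0.41 × 0.59) + 1/(27 × 0.32 × 0.68) = 0.153 + 0.170 = 0.323, so the standard error is 0.569. The 99% limits are the estimate divided and multiplied by exp(2.576 × 0.569) = 4.3. Such a band would say almost nothing about the treatment effect.

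**The case against.** **The kPa reading.** A reader might infer that, because the trial works in kPa, every patient lands in the first band and the interaction cannot be estimated. That would follow from coding the bands literally on kPa data. But the match between 150 and the entry limit makes the intended unit plain, so this part is a missing label and not a broken analysis.

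**Which ratio is meant.** The Day 0 list in 3.3 names the qualifying ratios in its PaO₂/FiO₂ entry. If those were the values banded, every eligible patient would be at or below 20 kPa and there would be no upper gap. This stands in part: the variable is not named beyond doubt. Against it are the general Day 0 rule in 3.3 and the separate rows in 8.3, which both point to the last value before randomisation.

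**Timing.** The 8 to 24 hours cover randomising and giving the intervention together, so they are not all delay before randomisation. The remark that higher ratios "are permitted between the two trial inclusion ABGs" concerns the time before the second gas. It shows that the plan expects fluctuation, but it is no direct evidence about the value at randomisation. The 48 hours to consent are enough for the argument.

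**An almost empty lowest band.** A reader might also infer this. The SAP gives no distribution for its population, and the wider normal case above puts 92 patients there. Likely sparse is as far as the document allows.

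**Impact.** This is one of eight exploratory subgroups. The primary chi-square test does not use the bands, and the adjusted logistic model in section 7 takes baseline PaO₂/FiO₂ without them. This stands in full and limits the severity.

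**Conclusion.** The bands are wrong as written. They carry no unit, and they stop at the entry limit although the baseline ratio, on the better-supported reading, is a later value that can exceed it. That conclusion needs no assumption about the distribution.

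The number of patients affected cannot be read from the SAP. The 5% to 20% above the top band, and the 0% to 8% in the lowest, rest on another trial's mean and an assumed SD and shape, and should be quoted only as illustration. If the qualifying ratio was meant, the upper gap closes, and what remains is the missing unit, the unnamed variable and a probably thin lowest band.

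Severity is minor to moderate: one exploratory analysis is affected, and the primary analysis and sample size are not.

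**What to change.** In 7.1 and the Appendix 3 shell:

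1. State the unit as mmHg with a conversion and rounding rule, or give the cut-points in kPa (6.67, 13.33, 20.00).
2. Name the ratio that is banded: the last before randomisation, or the second qualifying one.
3. If it is the last before randomisation, add an open category above 150 mmHg (above 20 kPa) and make the edges contiguous. If it is the second qualifying ratio, the present ceiling is adequate, because that value is at or below 20 kPa for every eligible patient; a rounding rule is still needed at 20.0 kPa.
4. Optionally, merge the lowest band with its neighbour, or test the interaction on the continuous ratio and keep the bands for display. The plateau pressure, PaCO₂, driving pressure and APACHE II subgroups already use quartiles or quintiles, which leave nobody out.

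The cost is a few lines of SAP and table-shell wording. Sections 3.3 and 8.3 show that both ratios are already collected, so no new data are needed. The choice should be recorded before any analysis of outcome by arm.

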5. SAMPLE SIZE CALCULATIONS

The required sample size is 1120 patients. With 90% power at a p value of 0.05 with a 3% dropout, 560 per group will be required to detect a 23% relative reduction (9% absolute reduction) in 90 day mortality, assuming a control group mortality of 41%. This sample size would also detect a 20% relative reduction (8% absolute reduction) at 80% power.

We have used two independent sources for the estimation of the all-cause mortality that was used to determine the sample size:

- 1. Data from the Intensive Care National Audit and Research Centre (ICNARC) case mix programme (CMP) for UK intensive care patients. The unpublished ICNARC data from the CMP for the year 2012 was compiled from 133,266 admissions from 203 adult critical care units in England, Wales and Northern Ireland. For patients with a PaO_2/FiO_2 ratio < 20kPa the ICU mortality was 40.7% and the hospital mortality was 48.8%.
- 2. Data from the NIHR HTA funded OSCAR trial (30). This was a recent large randomised controlled trial on high frequency oscillatory ventilation (HFOV) in patients with respiratory failure. The 30-day mortality in the control group in the OSCAR trial was 41.1%. These patients received conventional ventilation with a tidal volume of 6-8ml/kg PBW and had an average PaO₂/FiO₂ ratio of 15kPa.

Doc No: ST06-RD01 Page **14** of **35** We have assumed 90-day control group mortality will be at least equivalent to 41%. We have

used the effect size of one of the few interventions to reduce mortality in patients with

hypoxaemic respiratory failure. The ARDSNet ARMA trial demonstrated a 9% absolute risk

reduction in patients with hypoxaemic respiratory failure secondary to ARDS with lung

protective ventilation. Our hypothesis is that we can extend the benefits of more protective

lung ventilation with the use of ECCO₂R. Loss to follow up in UK critical care trials is low. We

know this is approximately 3% from previously published research as well as from the

experience of our team in managing large critical care trials in the UK.

An independent statistician (for the DMEC) will conduct an interim analysis for the primary

outcome measure (mortality) before the recruitment of 560 patients; (half the estimated

sample size), to ascertain whether the assumptions made in the sample size calculations are

correct.

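### Four continuous effect modifiers are analysed only by sample quartiles or quintiles; adding a prespecified continuous interaction would recover power if the treatment effect changes steadily with the modifier (CONSIDER)

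*SAP*

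**What the plan says.** Section 7.1 of the SAP labels the subgroup analyses exploratory, reports them with 99% confidence intervals, and uses logistic regression with treatment-by-subgroup interaction terms. Four of the eight listed modifiers are continuous baseline measures defined by sample quantiles:

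- plateau pressure: "Baseline Plateau Pressure prior to randomisation quartiles"
- PaCO2, also in quartiles
- driving pressure: "Baseline driving pressure prior to randomisation quartiles"
- APACHE II: "Baseline risk of death score (Apache II) quintiles prior to randomisation"

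No cut-points are given for these four. PaO2/FiO2 and centre volume, in the same list, do have fixed cut-points. The draft subgroup figure in Appendix 3 has one row per quartile or quintile, with an odds ratio and 99% CI. The SAP states neither the degrees of freedom nor the form of the interaction test, and nowhere plans a continuous, trend or spline version. Section 7 names baseline plateau pressure as an adjustment covariate in the secondary analysis of mortality and does not mention categories there.

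**The concern.** An interaction between treatment and an unordered 4- or 5-level factor spends 3 or 4 degrees of freedom, ignores the order of the categories and discards the variation within them. If benefit changes steadily across the range of, say, plateau or driving pressure, this is an inefficient way to look for it, and interaction tests in a trial sized for its main effect are weak already. A real gradient could be missed, and the reader would be left with four or five wide intervals in which chance patterns are easily seen.

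**Working it through.** **The plan's own figure.** The SAP gives no power for the interactions; its only sample-size figure is for the primary outcome. Inputs from section 5: "With 90% power at a p value of 0.05 with a 3% dropout, 560 per group will be required", for a "23% relative reduction (9% absolute reduction) in 90 day mortality", with control mortality of 41%. Take a 23% relative reduction, so p2 = 0.41 × 0.77 = 0.3157, with mean p̄ = 0.36285, and let the test be two-sided (assumed):

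n per arm = [1.960·√(2p̄(1−p̄)) + 1.282·√(p1(1−p1) + p2(1−p2))]² / (p1−p2)² = 545 (rounded up). Dividing by 0.97 gives 562 per arm, or 1124 in total, against the stated 1120. The figure reproduces to within rounding. After 3% dropout, 1120 × 0.97 ≈ 1086 patients are analysable.

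**Information kept by grouping.** Assume a normally distributed modifier (not stated in the SAP). The share of its variance lying between k equal groups is R = (1/k)·Σ m_j², where m_j is the mean of the standard normal in group j.

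- Quartiles: m = ±0.325, ±1.271; R = 0.861
- Quintiles: m = 0, ±0.532, ±1.400; R = 0.897

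**Power of the categorical test.** Assume an interaction linear on the logit scale that a continuous 1-df term detects with 80% power. The noncentrality is λ = 7.85 at the 5% level and 11.68 at the 1% level (the level that corresponds to a 99% CI). The categorical test has noncentrality λR on k−1 df.

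| Analysis | λ at 5% | Power, 5% level | Power, 1% level |
|---|---|---|---|
| Continuous, 1 df | 7.85 | 80% | 80% |
| Spline, 2 df | 7.85 | 71% | 71% |
| Quartiles, 3 df | 7.85 × 0.861 = 6.75 | 57% | 54% |
| Quintiles, 4 df | 7.85 × 0.897 = 7.04 | 54% | 51% |

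With the categorical test at the 5% level, getting back to 80% power would take about 1.61 (quartiles) or 1.70 (quintiles) times the patients.

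**The same groups as a 1-df trend.** With scores 1, 2, 3 and so on, the retained share is 0.856 (quartiles) or 0.888 (quintiles), and power at the 5% level is 74% or 75%. With the group means as scores it is 74% or 76%. The loss is about 4 to 6 points, so most of the drop in the table comes from the extra degrees of freedom and little from the grouping.

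**Check by simulation.** Logistic likelihood-ratio tests at the 5% level with n = 1086, mortality 41% v 32%, a prognostic log odds ratio of 0.3 per SD (assumed) and 1200 replicates:

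| Interaction (log OR per SD, assumed) | Continuous | Quartiles | Quintiles |
|---|---|---|---|
| 0.20 | 32% | 19% | 17% |
| 0.30 | 60% | 38% | 36% |
| 0.37 | 78% | 53% | 51% |

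**Other shapes, same simulation.** For one U-shaped interaction the linear term had 6% power, against 35% for quartiles. For a step at the top quartile the figures were 57% and 61%.

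**Width of the display rows.** A quartile holds 1086/8 ≈ 136 patients per arm. At 41% v 32% the standard error of the log odds ratio is √[1/(135.75 × 0.41 × 0.59) + 1/(135.75 × 0.32 × 0.68)] = 0.254. Then exp(2.576 × 0.254) ≈ 1.92, so each 99% CI runs from OR/1.92 to OR × 1.92.

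**The case against.** The best case for the plan has four parts.

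1. **The test form is not fixed.** A reader might infer that the SAP commits to tests on 3 or 4 degrees of freedom and so gives up a large part of their power. It does not say so. The one-row-per-category figure makes that the more natural reading, but a trend score is compatible with the text and would cost only a few points. This stands, and it makes the loss conditional.
2. **The plan sets no testing goal here.** The analyses are exploratory, the draft subgroup table has a 99% CI column and no p-value column, and section 7 assigns a significance level only to the primary outcome. No interaction power is claimed, so none is missed. This stands and bears on severity. The wide intervals are still a reason to show a more informative summary.
3. **No gradient hypothesis is stated.** A reader might take the trial's rationale to be that benefit rises with plateau or driving pressure. Section 5 speaks of extending the benefits of protective ventilation but gives no direction or shape for any modifier, and nothing suggests a monotone effect for PaCO2 or APACHE II. The linear gradient is therefore an assumption of the calculation, and it is the case that most favours a linear term. With a U-shape the categorical test wins clearly.
4. **Sample quantiles are a legitimate rule.** They are prespecified, use baseline values only and give cells of similar size. That the cut-points are unknown in advance is a minor reporting matter, met by publishing them.

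**Conclusion.** The point holds in a limited form. For four continuous modifiers the SAP plans only a quantile-group analysis, most naturally a categorical one. Under a linear gradient on the logit scale and a roughly normal modifier, that turns 80% power into about 57% (quartiles) or 54% (quintiles) at the 5% level, a loss of 23 to 26 points. Under a 1-df trend score the loss is about 4 to 6 points, and under a U-shaped effect the categorical test is the better one. A spline gives about 71% under the linear gradient, so once non-linearity is allowed for, the gain over quartiles is about 14 points (71 − 57).

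Nothing in the SAP is contradictory on this point, and neither the primary analysis nor its conclusion is touched. Severity: CONSIDER.

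**What to change.** In section 7.1, for plateau pressure, PaCO2, driving pressure and APACHE II, add:

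- a treatment interaction with the modifier as a continuous linear term (1 df), named as the main summary of that interaction;
- a restricted cubic spline version with prespecified knots (three knots give 2 df), reported alongside whatever the linear result, so that the choice between them is not made after seeing the data;
- a plot of the treatment odds ratio against the modifier with its 99% CI.

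Keep the quartile and quintile rows in the Appendix 3 figure for display, with the observed cut-points printed.

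The cost is SAP wording and a few lines of code; all four are baseline measures that the planned analysis already needs. The downside is that the linear term alone can miss a non-monotone interaction, which is why the spline and the display rows should stay beside it.
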